18.0 Withdrawal of Subjects

N/A: This study is not enrolling subjects. This section does not apply.

18.1 Describe anticipated circumstances under which subjects may be withdrawn from the research without their consent.

If a subject misses more than 3 treatment sessions, or if they have adverse events deemed unacceptable by an investigator.

18.2 Describe any procedures for orderly termination.

NOTE: Examples may include return of study drug, exit interview with clinician. Include whether additional follow up is recommended for safety reasons for physical or emotional health.

Subjects who miss an appointment will be contacted via telephone (and email if needed). If possible, they will be allowed to make up the missed session. If they are withdrawn from the study without consent, they will be contacted via phone. If phone contact cannot be made, an e-mail informing them of the withdrawal and the reason will be sent by the PI.

18.3 Describe procedures that will be followed when subjects withdraw from the research, including retention of already collected data, and partial withdrawal from procedures with continued data collection, as applicable.

Demographic information and the reason for withdrawal (if known) will be reported for all subjects who enroll in the study. Subjects who withdraw from the treatment will be allowed to continue with the self-reported data collection, however, only data from those who complete 80% of the treatment will be included in the primary analysis. Subjects who officially withdraw or are lost to follow-up after finishing the treatment sessions will be included in the analysis, as appropriate. For example, subjects who complete the 3-month follow-up, but not the 6 month or 1-year follow-up will be included in the 3-month analysis. Data collected for subjects who withdraw will be secured and retained in the same way as subjects who do not withdraw.

18.4 Describe what will happen to data already collected.

Data collected for subjects who withdraw will be secured and retained in the same way as subjects who do not withdraw.

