4.0 Study Design

4.1 Describe and explain the study design (e.g. case-control, cross-sectional, experimental, interventional, longitudinal, and observational). Indicate if there is randomization, blinding, control group, etc. If randomizing, explain how this will be achieved. For studies that have a complex study design (i.e., multiple arms and treatments), include a schematic diagram.

This study will have a pilot phase and a randomized phase. The pilot phase will include 1-3 subjects who will receive real rTMS and rehabilitation. Subjects in the placebo controlled randomize phase will receive rehabilitation combined with either real or sham rTMS. Randomization will be performed in REDCap and be stratified by upper or lower extremity. Randomization will occur in blocks of 4 to ensure equal distribution. Patients and the physical therapists delivering rehabilitation will be blinded to group allocation (real/sham rTMS). The researcher administering the rTMS will not be blinded.

Changes included in protocol version 2:

- Addition of new advertisement document that will be handed out by clinicians to potential subjects.
- Addition of a pilot phase that will include 1-3 unrandomized subjects.
- Adjusted the subject numbers to reflect the pilot phase subjects.
- Added [name] to the study team.
- Created new informed consent document for the pilot phase.

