5.0 Data Management and Analysis

5.1 Describe the data analysis plan, including any statistical procedures. This section applies to both quantitative and qualitative analysis

- 1) Primary: NPRS weekly average: 2-way ANOVA for within and between effects.

Secondary:

- 2) NPRS worse/least 24 hours: 2-way ANOVA for within and between effects.
- 3) NPRS number reaching 30% improvement: Descriptive (%), Logistic Regression
- 4) PROMIS: 2-way ANOVA for within and between effects.
 - a. Pain interference
 - b. Pain behavior
 - c. Physical functioning

- d. Satisfaction with discretionary social activity
 - e. Satisfaction with social roles
 - f. Fatigue
 - g. Depression
 - h. Anxiety
 - i. Anger
- 5) GROC: 2-way ANOVA for within and between effects.
 - 6) GROCi: 2-way ANOVA for within and between effects.
 - 7) PASS: Logistic Regression
 - 8) Grip Strength: 2-way ANOVA for within and between effects.
 - 9) 1 Repetition Max Leg Press: 2-way ANOVA for within and between effects.

5.2 *If applicable, provide a power analysis for the number of subjects to be included. If qualitative research, so state, and provide general justification for the total number of subjects proposed.*

NOTE: This may not apply to certain types of studies, including chart/records reviews, survey studies, or observational studies. This question is asked to elicit whether the investigator has an adequate sample size to achieve the study objectives and justify a conclusion.

The pain numeric rating scale (NPRS) MCID ranges from 1 to 2.5 in the literature. Salaffi et al (2003) found that a reduction of 2.0 points was associated with a rating of “much better” for patients with chronic pain. A review of the literature looking at pain ratings for patients with CRPS showed standard deviations approximately 1.0 to 2.0. Effect size was calculated using a 2-point NPRS change and a standard deviation of 1.7. G*Power 3.1.9.7 was used to calculate the sample size based on a repeated measures ANOVA with between and within measures comparisons. A partial η^2 of .07 (moderate effect size) gave an effect size of .274, $\alpha=0.05$, and power was set at 80%. Sample size was calculated for 2 groups, 4 measurements, with a correlation of .5, and nonsphericity of 1. This resulted in a group size of 10 participants for a total of 20 subjects. To account for dropouts up to 36 subjects will be enrolled in this study.

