 - Week 3- Mirror therapy (third component of GMI), add meditation, assess knowledge and update education as needed, progress graded activity 1 and 2, and add 3rd graded activity if appropriate based on patient goals.
 - Week 4- Continue with week 3 activities. Discuss experience with meditation and progress graded activity as tolerated.
- Pilot Testing
- This is a new treatment protocol for our lab. To test and adjust the logistics of the protocol 1-3 subjects will be enrolled as pilot subjects. The subjects will complete the standard protocol but will not be randomized. All 1-3 subjects in the pilot testing will receive the real rTMS.

11.1 Describe what data, including long-term follow-up, will be collected.

NOTE: For studies with multiple data collection points or long-term follow up, consider including a schedule or table in your response.

Measurements:

- The first visit
 - All instruments except the GROC
 - Basic demographics and other relevant medical information will be collected at this visit
- The last visit of each week
 - All outcome instruments will be collected
- All outcome instruments will be collected at 4-time points after the termination of the interventions-via REDCap e-mail survey or mailed survey if the subject does not have access to e-mail.
 - 4 weeks
 - 3 months
 - 6 months
 - 1 year

List, and upload, any instruments or measurement tools used to collect data (e.g. survey, scripts, questionnaire, interview guide, validated instrument, data collection form).

All of the listed instruments will be uploaded with this IRB submission.

- Numeric Pain Rating Score (0-10): Weekly average and worst and least pain intensity over past 24 hours
- NIH Patient-Reported Outcomes Measurement Information System (PROMIS): Pain interference, pain behavior, physical functioning, satisfaction with discretionary social activity, satisfaction with social roles, fatigue, depression, anxiety, and anger.
- CRPS Severity Score
- Patient Global Impression of Change (GROC) (only measured at follow-up)- scale rated from -7 (a very great deal worse) to +7 (a very great deal better) with 0 being about the same.
- Patient Acceptable Symptom State (PASS): Considering all the different ways your pain symptoms are affecting you, if you were to stay in this state for the next few months, do you consider that your current state is satisfactory?" (Yes/No)
- Adverse events

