12.0 Study Timelines

12.1 Describe the anticipated duration of the study needed to enroll all study subjects.

Study enrollment is anticipated to take 2 years. If subject numbers have not been met at 2 years, but we continue to have consistent enrollment, the study period may be extended.

12.2 Describe the duration of an individual subject's participation in the study. Include length of study visits, and overall study follow-up time.

Study visits will occur over a 4-week period. Subjects will be seen for 4 visits the first week and then 2 visits a week for the remaining 3 weeks (total of 10 visits). The first visit will take approximately 2.5-3 hours and subsequent visits will be approximately 1.5 hours in duration. Subjects who fail to attend approximately 80% of the visits (miss more than 2 sessions) will be removed from the study and treatment will be stopped.

12.3 Describe the estimated duration for the investigators to complete this study (i.e. all data is collected and all analyses have been completed).

Approximately 3.5 to 4 years. 1-2 years for study enrollment, 1-year follow-up, and up to 6 months for analyses.

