13.0 Research Setting

13.1 Describe all facilities/sites/locations where you will be screening and conducting research procedures. Include a description of the security and privacy of the facilities (e.g. locked facility, limited access, privacy barriers). Facility, department, and type of room are relevant. Do not abbreviate facility names.

Example: "A classroom setting in the New Academic Building equipped with a computer with relevant survey administration software", "The angiogram suite at University Hospital downtown campus", The Clinical Research Unit in the Institute for Human Performance."

Initial study screening will be conducted via telephone. Consent, initial data collection, and rTMS treatment will occur at the Motion Analysis Lab at the Institute of Human Performance. Rehabilitation sessions will be administered at the rehabilitation gym on the second floor of the Institute of Human Performance. During the 4-week treatment sessions, instruments will be completed electronically after the rehabilitation sessions on the second floor of the Institute of Human Performance. Measurements after the 4-week treatment sessions will be administered electronically.

13.2 For research procedures being conducted, for this study, external to Upstate (e.g., in schools, out-of-state, internationally, etc.) describe:

- Site-specific regulations or customs affecting the research
- The composition and involvement of any community advisory board
- Local scientific and ethical review structure outside the organization.
- Local issues affecting the research and rights of research subjects.

NOTE: This question is not referring to multi-center research. If this research is being conducted internationally, Supplemental Form E must be completed and uploaded.

N/A: This study is not conducted outside of Upstate.

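### The primary analysis keeps only subjects who complete 80% of treatment and no all-randomised analysis is planned, so the real-versus-sham comparison can be biased in either direction

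*Combined protocol and SAP*

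**What the plan says.** Section 11.0 places randomisation in the first session, ahead of baseline measurement and the first stimulation. Section 18.3 then sets the analysis population: "only data from those who complete 80% of the treatment will be included in the primary analysis". The same section provides that "Subjects who withdraw from the treatment will be allowed to continue with the self-reported data collection", but those data do not enter the primary analysis. Its allowance for people lost to follow-up covers only those who have already finished treatment.

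Section 5.1 gives the primary analysis as "NPRS weekly average: 2-way ANOVA for within and between effects". It names no analysis set, missing-data method or sensitivity analysis, and no other section does so.

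Four further provisions bear on the point:

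- **Missed sessions.** Section 12.2 removes a subject from the study, and stops treatment, after more than 2 missed sessions. Section 18.1 sets a different trigger: "If a subject misses more than 3 treatment sessions".
- **Blinding (4.1).** "Patients and the physical therapists delivering rehabilitation will be blinded to group allocation". The person giving the stimulation is not blinded.
- **Where weekly scores are collected (13.1).** "During the 4-week treatment sessions, instruments will be completed electronically after the rehabilitation sessions".
- **Pilot subjects (11.0).** One to three people receive real stimulation. "The subjects will complete the standard protocol but will not be randomized".

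**The concern.** Completing 80% of treatment is something that happens to a subject after allocation. Randomisation makes the arms comparable at the start, but it does not make those who stay in one arm comparable with those who stay in the other.

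The protocol itself describes ways in which attendance could depend on arm and on symptoms. A subject who cannot tolerate stimulation may stop (11.0). An investigator may withdraw someone for adverse events (18.1). Rehabilitation may temporarily worsen symptoms (17.1). Sham is delivered at a much lower intensity, with little or no sensation expected (11.0).

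If subjects doing badly leave the real arm, the remaining real arm looks better than it was. If they leave the sham arm, the bias works against rTMS. The primary result would then compare selected adherers, and no planned outcome comparison would show whether a difference, or the lack of one, came from who stayed.

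**Working it through.** **1. The plan's own figure.** Inputs from 5.2: partial eta squared 0.07, 2 groups, 4 measurements, correlation 0.5, nonsphericity 1, alpha 0.05.

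- f = √(0.07/0.93) = 0.274
- λ = f²·N·m/(1−ρ) = 0.274² × 20 × 4/0.5 = 12.01, with 3 and 54 degrees of freedom
- Power is 0.81 at N = 20 and 0.76 at N = 18

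The stated total of 20 reproduces as a group-by-time test, so I read the ANOVA in 5.1 that way. Section 5.1 does not say so explicitly.

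**2. General form of the bias.** Let q be the share excluded in an arm, and g the mean improvement of completers minus that of excluded subjects.

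Bias = q(real)·g(real) − q(sham)·g(sham)

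With an assumed g of 2 points in both arms:

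- 33% excluded on real, 10% on sham: 0.33×2 − 0.10×2 = +0.46
- The reverse: −0.46
- 33% in each arm: 0

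**3. Illustration at this trial's size.** From 5.2: SD 1.7, 4 measurements, correlation 0.5. Assumed: 15 per arm, no true effect, 3 or 5 excluded in each arm. In one arm, exclusion follows a score that correlates r = 0.5 or 0.8 with the outcome. In the other arm it is random.

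Removing the k worst of n on that score shifts the retained mean by

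r × SD × k/(n−k) × (mean of the k largest of n standard normal values)

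For n = 15 the five largest expected values are 1.736, 1.248, 0.947, 0.715 and 0.515.

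- k = 3: 3/12 × 1.31 = 0.328
- k = 5: 5/10 × 1.03 = 0.516

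The SD of first-to-last change is 1.7 × √(2(1−0.5)) = 1.7, and last-visit pain correlates 0.5 with change. Selection on change therefore shifts change by the full amount, for example 0.516 × 0.8 × 1.7 = 0.70. Selection on last-visit pain shifts change by half of that.

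False-positive rates come from simulating the group-by-time F test on retained subjects, 40,000 trials per scenario (standard error about 0.001).

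| Exclusion follows | Excluded per arm | r | Spurious difference in change (formula) | False-positive rate: related loss in real / sham arm |
|---|---|---|---|---|
| Last-visit pain | 3 | 0.5 | 0.14 | 0.054 / 0.052 |
| Last-visit pain | 3 | 0.8 | 0.22 | 0.059 / 0.062 |
| Last-visit pain | 5 | 0.5 | 0.22 | 0.059 / 0.056 |
| Last-visit pain | 5 | 0.8 | 0.35 | 0.070 / 0.071 |
| Change in pain | 3 | 0.5 | 0.28 | 0.061 / 0.061 |
| Change in pain | 3 | 0.8 | 0.45 | 0.080 / 0.082 |
| Change in pain | 5 | 0.5 | 0.44 | 0.071 / 0.073 |
| Change in pain | 5 | 0.8 | 0.70 | 0.110 / 0.113 |

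Simulated differences agree with the formula to about 0.01 (range 0.13 to 0.71). The sign favours rTMS when the outcome-related loss is in the real arm, and sham when it is in the sham arm.

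**4. Patterns that do little harm.** The same outcome-related loss in both arms gives a mean bias of about 0 and a rate of 0.051 to 0.063. Loss that follows overall pain level gives no bias in change and a rate of about 0.05. Random loss gives neither bias nor inflation.

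**5. Power cost of analysing everyone.** Assume an effect rising linearly to 2 points at measurement 4, random loss, and NPRS collected from everyone. The group differences 0, 0.67, 1.33 and 2 give f = 0.373/1.7 = 0.219. The same formula then gives power 0.69 for 24 completers and 0.60 for 20. Simulated power for all 30 randomised:

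| Non-completers per arm | Benefit they keep | All randomised | Completers only |
|---|---|---|---|
| 3 of 15 | none | 0.57 | 0.69 |
| 5 of 15 | none | 0.40 | 0.60 |
| 3 of 15 | half | 0.70 | 0.69 |
| 5 of 15 | half | 0.62 | 0.60 |

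**6. The missed-session limits.** Ten sessions are planned: 8/10 = 80% and 7/10 = 70%. A subject who misses exactly 3 is removed under 12.2 but not under 18.1, and is outside the primary analysis either way unless a session is made up (18.2).

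**The case against.** The best defence is that the trial already limits selective loss. Patients and therapists are blinded, stimulation can be reduced or tried again on another day, and missed sessions can be made up. The protocol also promises to report participant disposition and reasons for withdrawal, which could expose unequal loss. These measures reduce the risk, but disposition tables are descriptive. They do not show what the treatment comparison would have been with everyone included.

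A second argument is that the numbers are modest and depend on assumptions. This is fair. The rate of 0.11 needs one-third exclusion, a correlation of 0.8 with change, and outcome-related loss in one arm only; the other scenarios lie between about 0.05 and 0.08. The illustration also uses the 4 measurements of the power calculation, whereas the schedule has a baseline and 4 weekly scores before follow-up begins. The choice of test matters too: a t-test on a single outcome, under similar assumed loss, gave shifts of about 0.3 to 0.6 points and false-positive rates of about 8% to 15%.

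Third, 5.1 does not say that incomplete cases are dropped. That is the usual default of a repeated-measures ANOVA, not a stated rule. Finally, the words primary analysis may imply that others exist, but none is specified.

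**Conclusion.** The concern holds and should be fixed before the analysis. The case rests on the structure of the plan: its only specified efficacy comparison conditions on an event after randomisation. The size and direction of the resulting bias cannot be known from the documents, which give no expected rate of failing the 80% rule. The enrolment ceilings of 30, 33 and 36 (2.1, 6.1 and 5.2) are not such a rate. In the assumed scenarios with one-sided, outcome-related loss, the largest spurious change is about a third of the target effect (0.71/2 = 0.36). The missed-session conflict is a separate inconsistency that does not by itself alter the analysis set.

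**What to change.** - **18.3:** define the primary analysis set as all randomised subjects in their allocated arm, whatever number of sessions they attended, and exclude the non-randomised pilot subjects. Keep the 80% set as a labelled per-protocol sensitivity analysis. State whether the 80% counts stimulation sessions, physical therapy sessions or both.
- **5.1:** replace the primary ANOVA with a linear mixed model for repeated measures (arm, time, arm-by-time) fitted to every available NPRS value, and state its missing-data assumption.
- **12.2 and 18.3:** separate ending treatment from ending data collection. Weekly scores are completed on site, so send them by REDCap e-mail survey, which the trial already uses for follow-up, to anyone who stops attending. The model cannot fully protect against outcome-related loss if these subjects give no data.
- **12.2 and 18.1:** reconcile the missed-session limits. Which one applies is for the investigators to decide.

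The cost is protocol wording, a different model and some extra surveys, plus possible dilution of the effect. If non-completers gain nothing from rTMS, a 2-point effect becomes 2 × 0.8 = 1.6 points at 20% non-completion and 2 × 2/3 = 1.33 at one third, and power falls below that of the completer set. If they keep half the benefit, power is about equal.

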11.0 Research Methods & Procedures

Provide a detailed description of the methods and procedures that will be used to carry out the study. Include a summary of study visits and procedures (i.e., schedule of events table) in the space below or as an attachment.

Please make sure to include:

- Dosing of drugs and other details of study drug administration and study treatments
- A list and description of any experimental procedures
- A list and description all tests & procedures that would not be done if the subjects were not in the study
- An explanation how study participation differs from the standard of care
- Procedures being performed to monitor subjects for safety or to minimize risks

Interventions: 4 weeks

- Treatment will start (week 1) with 4 consecutive rTMS and 2 PT sessions (skipping weekends)
- Sessions will continue at 2 times a week for a total of 10 sessions
- Measurements will occur at:
 - The first visit (except GROC)
 - The last visit of each week
 - At 4 time points after the termination of the interventions-via e-mail survey
 - 4 weeks
 - 3 months
 - 6 months
 - 1 year

First Session:

- Screening (Budapest Criterion, and TMS screening)
- Informed consent- during the phone screening subjects will be given the opportunity to have informed consent documents sent to them via email. Subjects will be given time to read the documents and ask questions about the study before agreeing to participate.
- Randomization
- Baseline measurements
- rTMS/sham rTMS session
- PT session

Subsequent Sessions (9):

- TMS screening
- rTMS/sham rTMS (the first week 2/4 sessions will not include a PT session)
- PT session
- Repeat measurements will be taken at the end of each week (4 in total)

Test and measures: All outcome measures are self-reported and collected using REDCap.

- Primary
 - Numeric Pain Rating Scale (NPRS) (0-10): Average score for the week

- Secondary Measures

- Numeric Pain Rating Score (0-10): Worse and least pain intensity over past 24 hours
- NIH Patient-Reported Outcomes Measurement Information System (PROMIS): Pain interference, pain behavior, physical functioning, satisfaction with discretionary social activity, satisfaction with social roles, fatigue, depression, anxiety, and anger.
- Patient Global Impression of Change (GROC) (only measured at follow-up)- scale rated from 0 (not important) to 7 (a very great deal important).

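### Section 5.1 does not say which occasions enter the repeated-measures ANOVA or how missing ones are handled, so keeping later leavers as 18.3 intends is left to the analyst

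*Combined protocol and SAP*

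**What the plan says.** - **Method.** Section 5.1 gives the primary analysis as "NPRS weekly average: 2-way ANOVA for within and between effects". The same method is named for most of the continuous secondary measures. No list of occasions, missing-data method, mixed model or imputation is given.
- **Sample size.** Section 5.2 confirms the type of ANOVA: "G*Power 3.1.9.7 was used to calculate the sample size based on a repeated measures ANOVA with between and within measures comparisons". It adds: "Sample size was calculated for 2 groups, 4 measurements, with a correlation of .5, and nonsphericity of 1". It does not say which four measurements are meant.
- **Schedule.** Sections 11.0 and 11.1 set a baseline measurement, one at the last visit of each of four weeks, and then more "At 4 time points after the termination of the interventions-via e-mail survey": 4 weeks, 3 months, 6 months and 1 year. For the NPRS that is 1 + 4 + 4 = 9 occasions.
- **Withdrawal.** Section 18.3 keeps subjects who are lost after finishing treatment in the analysis where appropriate. It illustrates this by saying that "subjects who complete the 3-month follow-up, but not the 6 month or 1-year follow-up will be included in the 3-month analysis". The same paragraph separately limits the primary analysis to those who complete 80% of treatment.

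**The concern.** A classical within/between ANOVA needs a value at every occasion in the model. A subject with one gap is removed from all of them. Section 18.3 wants the opposite: a subject who leaves after 3 months should still count at 3 months. Whether the planned analysis achieves this depends on which occasions form each ANOVA, and 5.1 is silent on that.

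Aim 2, the long-term effect, rests on surveys completed remotely for up to a year, where gaps are most likely. If the occasions are not fixed in advance, the analyst chooses them after seeing who has dropped out. In a trial of about 20 to 30 subjects, that choice can remove a large share of valid data.

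**Working it through.** **1. Reproduce the plan's sample size.** Inputs from section 5.2: partial eta squared .07, alpha 0.05, power 80%, k = 2 groups, m = 4 measurements, correlation .5, nonsphericity 1.

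- f = √(.07/.93) = .2744, which agrees with the stated .274.
- Noncentrality λ = f² × N × m × ε/(1 − ρ) = .274² × 20 × 4 × 1/.5 = .075076 × 160 = 12.01.
- df1 = (k − 1)(m − 1) = 3 and df2 = (N − k)(m − 1) = 18 × 3 = 54.
- Power is 0.811 at N = 20 and 0.759 at N = 18. The stated total of 20 is reproduced for the group-by-time interaction.

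**2. Who is kept under each reading of 5.1.** Assumed illustration: 20 subjects complete treatment, 4 leave after 3 months and 2 more after 6 months, with no other gaps.

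| Reading | Subjects kept |
|---|---|
| One ANOVA on all nine occasions | 20 − 4 − 2 = 14 |
| Separate ANOVA ending at 3 months, or baseline versus 3 months | 20 |
| Separate ANOVA ending at 6 months, or baseline versus 6 months | 20 − 4 = 16 |
| Separate ANOVA including 1 year | 14 |

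The first reading drops the four subjects whom 18.3 uses as its example. The separate ANOVAs keep them at 3 months.

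**3. What each per-horizon version costs.**

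- *Cumulative version.* An ANOVA running from baseline to 3 months has seven occasions: baseline, four weekly, 4 weeks and 3 months. A subject who answers at 3 months but missed any of the other six is still lost. This can happen within the plan's own rules: section 12.2 tolerates up to two missed sessions, and weekly scores are taken at the last visit of the week. Section 18.2 allows make-up sessions only where possible. Section 18.3 does not deal with gaps of this kind.
- *Baseline versus one follow-up.* Here m = 2, so λ = .075076 × 20 × 2/.5 = 6.01, with df 1 and 18. Power is 0.640 at N = 20, and 30 subjects are needed to pass 80% (0.826). This holds f at .274 and the correlation at .5, which is an assumption, because 5.2 gives them only for the 4-measurement design.

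**4. How many complete sets to expect.** The documents give no follow-up loss rate, so 5% and 10% per survey, independent over the four surveys, are assumptions.

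| Starting follow-up | 5% per survey | 10% per survey |
|---|---|---|
| 30 | 30 × .95⁴ = 24.4 | 30 × .90⁴ = 19.7 |
| 20 | 20 × .95⁴ = 16.3 | 20 × .90⁴ = 13.1 |

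The plan itself foresees loss. Its enrolment figures of 30 (section 2.1), 33 (6.1) and 36 (5.2), set against 20 completers, imply allowances of 1 − 20/30 = 33%, 1 − 20/33 = 39% and 1 − 20/36 = 44% for dropout of all kinds.

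**The case against.** A reader might infer that 18.3 cannot be carried out with the stated ANOVA. The documents do not support that. Section 18.3 itself speaks of an analysis at 3 months, which reads naturally as one analysis per time point. A group-by-time ANOVA restricted to that horizon is still the method in 5.1. Nothing in the documents puts all nine occasions into one model or states listwise deletion. The 4 measurements in 5.2, and the split into short-term and long-term aims, point away from a single nine-occasion ANOVA. This part of the objection stands.

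It is also fair that 20 is the wrong base for deducting loss. Section 6.1 aims for at least 20 subjects to complete all testing, so 20 is a target after dropout. The row for 30 is therefore the more natural one, and the row for 20 applies only if no more than 20 reach follow-up. If 20 do complete everything, a complete-case 4-measurement ANOVA keeps its 0.81 power, and the loss is confined to the data of those who answered only some surveys.

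A reader might further infer serious bias at 3 months from dropping later leavers. That is not shown. Take means of 6 and 4, SD 1.7, and leaving after 3 months with probability 60% above an NPRS of 5 and 10% otherwise. The 3-month difference among those who stay is then about 1.85 instead of 2.0. Under the per-horizon reading the leavers remain in the 3-month comparison and this shift does not arise.

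What the objection leaves open is that 5.1 does not state the per-horizon reading, does not say which version is meant, and gives no rule for a missed intermediate occasion.

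**Conclusion.** The point holds as under-specification with a cheap and better alternative; 18.3 is not an impossible rule. Sections 5.1, 5.2 and 18.3 together do not fix which occasions form each ANOVA or what happens to incomplete subjects. Each available reading has a cost:

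- all nine occasions at once conflicts with the intent of 18.3;
- a cumulative ANOVA loses subjects with an earlier gap;
- baseline versus one follow-up departs from the powered design, at 0.64 against 0.81.

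The power figures rest on the plan's f, correlation and sphericity. The counts of complete subjects rest on assumed loss rates. The matter should be settled before data are analysed, but it does not threaten the trial's validity by itself.

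**What to change.** **In 5.1**, replace the 2-way ANOVA for repeated continuous outcomes with a linear mixed model for repeated measures: REML, time as a category, group, group-by-time, a simple covariance structure and a small-sample degrees-of-freedom correction, using every available observation. List the occasions in the model and take the contrast at each time point from it.

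**In 18.3**, state that subjects in the analysis set who leave after treatment contribute all data up to leaving. The separate 80%-of-treatment restriction is not changed by this wording. Report the number contributing at each time point by arm.

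**In 5.2**, say which four measurements were meant. The 0.81 belongs to the test over four measurements and should not be quoted for a contrast at a single time point.

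The cost is a few sentences and standard software. The downside is that, at this sample size, the covariance structure must be kept simple and the degrees-of-freedom correction is needed. The model also assumes that loss depends only on what has been observed. If the sponsor prefers to keep the ANOVA, the minimum is to list the occasions in each analysis and the rule for missed ones; this removes the ambiguity but not the loss of incomplete subjects.
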